The patient will attend the clinic for three separate visits each approximately one week apart. starting with phasing 'without heat', then phasing 'with heat' and lastly phasing wearing the Blephasteam mask but with no heat as a control. The Blephasteam mask will only be used on the days of the clinic visits, the participants will not be required to use the device at home. The water carrier inserts for the masks will be designated to the same patient throughout the study for hygiene reasons. The inserts for the mask will be moistened and fitted according to the manufacturers' instructions. The wireless device will be left to reach temperature for 3-4 minutes then the patient will be asked to wear the mask and be instructed to keep their eyes closed, this occurs once at the start of each visit. The device warms the ocular surface for a set time of 10 minutes, after which the participants will remove the mask and instil their habitual Glaucoma eyedrops. They will be instructed to close their eyes and apply light pressure on the inner corner of the eye for 30 seconds. The IOP will then be measured at the first time point with the ORA and Goldman devices. Although both eyes will be treated with the heat mask only the right eve results (to eliminate bias) will be used for the statistical analysis. During the visits the patients' will have their best corrected visual acuity (BCVA) reviewed before and after measurements are taken. IOPs are measured first using the ORA tonometer (Reichert Inc., Germany) followed by the Goldman tonometer (Haag-Streit AG, Switzerland) five minutes later as per previous studies measuring IOP with the sequential use of tonometers (Tejwani et al., 2015). These IOP measures are taken at five set time points during the day called 'phasing': 08:30 +/- 30 mins, 10:30 +/- 30 mins, 12:30 +/- 30 mins, 14:30 +/- 30 mins and 16:30 +/- 30 mins. An average of three measures will be taken using the ORA machine, when using the Goldman tonometer three measures will only be taken if the first two are not within >2mmHg of each other. The procedure for the Goldman tonometer will be as follows: Two individuals (an operator and a reader) will perform the readings for the study visits. The operator will be responsible for operating the slit lamp, tonometer, and the instrument dial, while the reader will read and record the results. A full anterior segment slitlamp examination will be performed at the end of each phasing visit to ensure there are no adverse effects experienced following the treatment, including grading of the Meibomian glands (Efron scale). Additional assessments include adverse events and quality of life and ocular questionnaires.

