
One to two weeks after completion of the study the patients will undergo a further visual

fields test (Humphrey sita fast 24-2) to ensure no significant progression of their disease has occurred as a result of the study regime. All data will be recorded and stored for analysis at the end of the trial and made available to the standard of care treating clinician. At the end of the trial the patients will continue their Glaucoma visit schedule as requested by their treating Ophthalmologist.

All attempts will be made to have participants complete the study by organising visits that fit in with their timetable and offering further appointments should the participant not be able to attend on a certain day. Participants will be offered reimbursement for travel and refreshments on the day of their study visits. In the case of participant 'drop-outs', the research team will attempt to recruit further participants otherwise patients on whom all the tests could not be performed will be excluded from analysis.

When designing this trial, it was important for us to ensure that the comments and suggestions of the public and patients were taken on board, so that we could confirm that this trial was suitable for people with POAG or OHT. To do this, a patient and public involvement (PPI) forum was be organised on 30th May 2023 and the trial subsequently developed with the help of people diagnosed with Glaucoma in the Cambridgeshire area who agreed that the tests and procedures included in this study were practical and acceptable to patients.

It is the intention of the research team that the results of the study will be disseminated in peer-reviewed articles and at ophthalmic conferences.

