## **5.2 Statistical Methods**

## 5.2.1 General:

Data will be presented using descriptive statistics; continuous data will be summarised using means & standard deviations if normally distributed otherwise using median and interquartile

Version 1.0 13/JUN/2023

range. For categorical data frequencies and percentages will be reported. Missing data will be reported.

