## 7.2.1 Size of sample

This is a feasibility study and as such a sample size of 24 participants has been selected for this quantitative research and this has been based on the figures previously cited by Sim and Lewis (2012) and Julious (2005) and also taking into account the budget available for equipment. The average of the IOPs measures taken at each time point with the ORA or Goldman tonometer and with and without the addition of heat will be used for statistical analysis.

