## General

There are four visits that the participants need to undergo in excess of standard of care. Standard care of clinic appointments in the Glaucoma clinic will be continued as normal. The

precise risks and benefits of participating in the study will be outlined in patient information sheets.

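### The all-tests exclusion rule can discard participants who already have the primary IOP pair, and it makes no exception for safety

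*Protocol*

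**What the plan says.** Section 5 deals with drop-outs in one sentence. It first says that "the research team will attempt to recruit further participants", and then gives the fallback: "otherwise patients on whom all the tests could not be performed will be excluded from analysis". The rule is not limited to IOP, to the primary comparison or to efficacy. The only other statement on incomplete data is in section 5.2.1: "Missing data will be reported".

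The workload behind the phrase on all tests is large. Section 5 states: "The patient will attend the clinic for three separate visits each approximately one week apart". The order is the same for everyone: no heat, then heat, then the unheated mask. IOP is taken at five times per visit with two tonometers. The schedule of procedures adds questionnaires, slit-lamp examination, gradings and visual acuity at each phasing visit, and a safety visit with visual field and acuity. Section 8 (General) confirms: "There are four visits that the participants need to undergo in excess of standard of care".

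The primary objective (section 4.1.1) needs much less: right-eye IOP at baseline and after heat, compared by a paired test (section 5.2). The schedule shows no IOP at the consent visit, so baseline IOP is taken here to mean visit 1.

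On size, section 7.2.1 says "a sample size of 24 participants has been selected for this quantitative research", based on pilot-study references and "also taking into account the budget available for equipment". No drop-out allowance is given.

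**The concern.** The rule asks for far more than the primary comparison uses. Because the visit order is fixed, someone who leaves after the heat visit has already supplied both halves of the primary pair. If that person left because of the heat, the rule removes an observation that is both valid and informative.

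Three things are at stake. The estimated heat effect can lean towards people who tolerate the procedure. Precision is lost from a sample that is small to begin with. And although the title names safety and section 4.1.2 lists adverse events as a secondary objective, no safety population is defined and the exclusion has no stated safety exception, so a person who stops after an event could fall out of the adverse-event summary. In a feasibility study, who completes and why is also a result in its own right.

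**Working it through.** **Plan's own figure.** N = 24 cannot be reproduced by a formula: the protocol gives no SD, power or drop-out rate. It is taken as stated.

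**Inputs from the protocol.** N = 24; three phasing visits and one safety visit; 3 visits × 5 times × 2 tonometers = 30 IOP assessments; effect of interest 1.5 mmHg and threshold P < 0.05 (section 5.2.2; two-sided assumed).

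**Assumptions.** The miss rate *m* is not given, so a range is used. The SD of paired differences is not given; 3 mmHg is used, with 2.5 and 3.5 as a range.

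**1. Complete cases when whole visits are missed.** All-tests rule: 24 × (1 − m)^4. Primary pair only (visits 1 and 2): 24 × (1 − m)^2.

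| m per visit | All-tests rule | Primary pair available | Pair available but excluded, as a share: 1 − (1 − m)^2 |
|---|---|---|---|
| 2% | 24 × 0.98^4 = 22.1 | 24 × 0.98^2 = 23.0 | 4% |
| 5% | 24 × 0.95^4 = 19.5 | 24 × 0.95^2 = 21.7 | 10% |
| 10% | 24 × 0.90^4 = 15.7 | 24 × 0.90^2 = 19.4 | 19% |

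**2. Complete cases when single readings are missed independently.** 24 × (1 − m)^30: at 1%, 24 × 0.740 = 17.8; at 2%, 24 × 0.545 = 13.1. This is pessimistic, because misses cluster within visits and the two tonometers are used at the same sitting. If one tonometer suffices (15 readings), the figures are 24 × 0.860 = 20.6 and 24 × 0.739 = 17.7.

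**3. Precision if replacement fails.** The 95% CI half-width is t × SD/√n; power is from the noncentral t for 1.5 mmHg. At SD 3 mmHg:

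| n analysed | Half-width (mmHg) | Power |
|---|---|---|
| 24 | 1.27 | 0.650 |
| 22 | 1.33 | 0.609 |
| 20 | 1.40 | 0.565 |
| 16 | 1.60 | 0.465 |

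From 24 to 16 the interval widens by 1.60/1.27 − 1 = 26%. At SD 2.5, power falls from 80% to 61%; at SD 3.5, from 52% to 36%.

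**4. Possible bias.** The mean among those retained differs from the mean among all with the pair by f × D, where f is the share with the pair who are excluded and D is the difference in heat effect between retained and excluded. With D assumed at 2 mmHg: 0.10 × 2 = 0.20 mmHg at m = 5% and 0.19 × 2 = 0.38 mmHg at m = 10%, the latter about a quarter of 1.5 mmHg. If missingness is unrelated to the effect, D = 0 and there is no bias.

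**The case against.** The sentence opens with drop-outs and ties exclusion to failed replacement. It could be meant only for people who left early, not for someone missing one afternoon reading; taken literally, it could even mean people on whom no test was done. The plain reading is that not all tests were done, but the ambiguity is real. It argues for rewriting the sentence, not for leaving it.

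Replacement also matters: if it succeeds, n stays near 24 and the loss of precision largely disappears. That stands. Replacement does not bring back the people lost, and recruits held to the same rule are selected in the same way.

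Some stronger inferences are not supported:

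- A reader might infer that the results will be biased. The documents do not show that missing tests relate to tolerance or response. The mask is worn for ten minutes once per visit, in clinic, and misses may be logistical.
- A reader might infer that adverse events in drop-outs will vanish. Section 5.2 allows a full listing, and section 5.2.2 tabulates events by receipt of heat, not by completion. The exclusion merely lacks a safety exception.
- A reader might infer that the completion rate is hidden. Section 5.2.1 says that missing data will be reported; what is not secured is a count of drop-outs with reasons.
- A reader might take 18 or 13 of 24 as the expected yield. That needs independent misses and failed replacement. Section 5 also offers further appointments to limit missed visits.

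Finally, a mixed model is not already part of this plan, which specifies paired tests and repeated-measures ANOVA, and it would not by itself remove bias if people leave because of unrecorded intolerance.

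**Conclusion.** The point holds as a defect in a stated rule, not as a detail left to the SAP. On its plain reading, section 5 excludes participants who have everything the primary comparison needs, and it makes no exception for safety. Bias and understated adverse events are possible, not certain.

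The size rests on assumed miss rates. Clustered by visit at 2% to 10%, about 2 to 8 of 24 are incomplete, and roughly 1 to 4 of those have the primary pair and would be lost needlessly (23.0 − 22.1 = 0.9; 19.4 − 15.7 = 3.7). Independent misses of 1% to 2% per IOP reading lose about 6 to 11, as a pessimistic bound. The precision loss applies only where replacement fails. The case for changing the sentence does not depend on any one rate.

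**What to change.** Replace the exclusion sentence in section 5 so that it says:

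- Each comparison includes every participant with the right-eye IOP data it needs. The primary paired analysis requires visits 1 and 2 only; comparisons with the unheated mask also require visit 3. A mixed model on all available readings may be used for the repeated time points.
- Everyone who starts any phasing visit is included in the adverse-event and safety tables.
- Replacements may be recruited, but data from drop-outs are kept, and the number of drop-outs is reported with reasons.
- The analysis restricted to participants with all tests is kept as a sensitivity analysis.

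The primary and repeated-measures text in sections 5.2 and 5.2.2 needs a matching edit. No new data or visits are needed. The small cost is that the number analysed will differ between comparisons and must be shown for each.

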## 5.1 Data collection and recording

Baseline and follow-up data will be recorded on a Case Report Form (CRF). All CRFs will be stored in a secure cabinet and the data will be inputted into a password protected database. The names of patients who decline to take part or those who do not meet eligibility criteria will also be recorded in a secure database to ensure that they are not re-approached. Each participant will be assigned a unique trial ID number at the start of the assessment process. This number will be written on all clinical assessment forms, datasheets and databases used to record participant data. A hard copy of a record sheet linking patient identity, contact details and trial ID number for all participants will be kept at the sponsor site (North West Anglia Foundation Trust). This will be placed securely in a locked filing cabinet separate from datasheets. All data will be kept secure at all times and maintained in accordance with the requirements of the Data Protection Act and archived locally according to clinical trial good clinical practice (GCP) regulations and the host institutions additional procedures.

## **5.2 Statistical Methods**

## 5.2.1 General:

Data will be presented using descriptive statistics; continuous data will be summarised using means & standard deviations if normally distributed otherwise using median and interquartile

Version 1.0 13/JUN/2023

range. For categorical data frequencies and percentages will be reported. Missing data will be reported.

### Primary analysis:

1. Mean difference of IOP will be analysed using paired t-test if normally distributed or using Wilcoxon signed rank test for pared cases if not normally distributed.

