### 4.1 Objectives

### 4.1.1 Primary objective:

1. The mean difference of IOP in the same eye (right eye) from the baseline IOP and after the bilateral heat intervention.

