## 5.2.2 Datasets

To determine whether there is a significant change in IOP in each participant, the IOP measured with and without the addition of heat over the five time points will be used in a one-way repeat measure ANOVA test will be completed for each day of phasing. A paired ttest will be used to establish significance between an individual's IOP measure at a certain time point with or without the addition of heat. A difference of 1.5mmHg in IOP mean deviation would be considered a significant change of IOP. This value has been used in previous Glaucoma studies (Allergan Bimatoprost SR and Thea In-Sight) to provide a 95% confidence interval. A paired t-test will be used to establish any significant change in BCVA at baseline and exit visit based on a mean SD change of 0.1 logMAR or 5 ETDRS letters. Ocular safety parameters, QoL (EQ-5D-5L) and OSDI questionnaires, visual fields and slit-lamp exam measures will be summarised for the cohort by mean, standard deviation (SD), median, minimum and maximum values. A non-parametric analysis (Wilcoxon signed rank test) will be used if the data is found to not be normally distributed. Ocular adverse events and safety variables will be tabulated by whether the participant has received heat treatment or not before instilling their anti-hypotensive eye drops. Normality of the data will be checked by plotting histograms of the data (separately before and after the heat) and not using stats tests. Differences will be considered statistically significant P values less than 0.05.

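### The primary analysis can swap the test of the mean IOP difference for a Wilcoxon test after a look at the outcome histograms, so the primary P value may not concern the stated endpoint

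*Protocol*

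**What the plan says.** Section 4.1.1 of the protocol defines the primary outcome as "The mean difference of IOP in the same eye (right eye) from the baseline IOP and after the bilateral heat intervention". Section 5.2.1 (Primary analysis) then gives two possible tests, saying that the mean difference will be analysed "using paired t-test if normally distributed or using Wilcoxon signed rank test for pared cases if not normally distributed".

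Section 5.2.2 says how the choice is made: "Normality of the data will be checked by plotting histograms of the data (separately before and after the heat) and not using stats tests". It gives no criterion for what counts as non-normal. The same section sets the benchmark ("A difference of 1.5mmHg in IOP mean deviation would be considered a significant change of IOP") and the significance level ("Differences will be considered statistically significant P values less than 0.05"), without saying whether the test is one- or two-sided.

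Section 5.2.1 (General) ties the reported summary to the same judgement: "continuous data will be summarised using means & standard deviations if normally distributed otherwise using median and interquartile" range. Section 7.2.1 sets the size: "a sample size of 24 participants has been selected for this quantitative research".

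**The concern.** The two tests do not share a target. The paired t-test asks whether the mean of the paired differences is zero. The Wilcoxon signed rank test asks whether those differences are distributed symmetrically about zero. The questions coincide for the mean only when the differences are symmetric, and visible skew is one of the main reasons a reader of a histogram would leave the t-test.

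The choice is also made after the outcomes are known. The histograms are drawn by condition, so whoever reads them knows which data are with heat, and no threshold binds the reading. The study is intended as proof of concept for a larger trial (sections 2 and 4.2). What that trial needs from it is a mean difference with a confidence interval, and on the Wilcoxon branch the protocol does not promise one.

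**Working it through.** **1. Stated level.** Taking one paired difference per participant, n = 24 and two-sided 0.05:
- the exact Wilcoxon signed rank null distribution gives a critical value of 81 and a size of 0.0491;
- the paired t-test with normal data gave 0.0495 in 20,000 simulated trials.

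Each test on its own holds the stated 0.05 when its assumptions are met.

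**2. Change of target.** As an assumed example with skewness 2, let the difference be SD × (E − 1), with E exponential with mean 1. The mean difference is 0. Wilcoxon responds to the pseudo-median, the median of the average of two independent differences. For E this is m/2, where e^(−m)(1 + m) = 0.5, so m = 1.678 and m/2 = 0.839. The pseudo-median is therefore (0.839 − 1) × SD = −0.161 × SD, or −0.48 mmHg if the SD is 3 mmHg. Wilcoxon tests a quantity that is not zero although the endpoint in section 4.1.1 is exactly zero.

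**3. When this cannot happen.** If heat does nothing and the two visits are exchangeable, the difference D has the same distribution as −D. It is then symmetric however skewed IOP is at each visit.

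**4. False-positive rate for the mean.** A visual check cannot be simulated, so Shapiro-Wilk P < 0.05 stands in for it. In the written form it is applied to each condition separately and the switch is made if either fails. The protocol gives no SDs or distributions, so all of these are assumptions. For skewed differences, baseline IOP is normal with SD 3 and the differences are mean-centred gamma.

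| True mean difference zero | Switch, written trigger | t-test alone |
|---|---|---|
| Normal | 5.0% | 5.0% |
| Skewed IOP, symmetric differences (switched in 74%) | 4.9% | 5.0% |
| Skewed errors, exchangeable visits (switched in 47%) | 5.1% | 5.0% |
| Heavy-tailed symmetric differences, t(3) | 4.6% | 4.3% |
| Skewness 1.0 / 1.4 / 2.0, difference SD 2 | 5.8 / 6.4 / 8.6% | 5.6 / 6.0 / 7.7% |
| Skewness 1.0 / 1.4 / 2.0, difference SD 3 | 6.5 / 7.4 / 9.3% | 6.1 / 6.4 / 7.5% |

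The excess due to the switch is 0.2 / 0.4 / 0.9 points at SD 2 and 0.4 / 1.0 / 1.8 points at SD 3. Repeat runs agreed to within about 0.4 points, so the smallest of these excesses are within simulation noise. If the trigger were applied to the paired differences instead, the switch would give 7.1 / 9.2 / 14.1% against 5.6 / 6.0 / 7.7%.

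**5. Power, in both directions.**
- Responder mixture: 25% of patients at −6 mmHg, so a mean of 0.25 × (−6) = −1.5, with noise SD 2. The t-test has 57%, the switch 55% with the written trigger and 52% with the trigger on the differences.
- Heavy tails: t(3) differences, scale 2, mean −1.5. The t-test has 64%, the switch 70% with the written trigger and 74% with the trigger on the differences, and Wilcoxon throughout 76%.

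**6. Reported estimate.** A non-normal reading moves the summary to median and interquartile range under section 5.2.1 (General). A difference in medians is not the mean difference to which the 1.5 mmHg benchmark in section 5.2.2 refers.

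**The case against.** A t-test with a Wilcoxon fallback is conventional, and in a 24-person feasibility study it rarely decides anything. The fallback also has a real use. With heavy tails or outliers Wilcoxon keeps its level and gains power, and dropping the switch gives up 6 to 10 points in the t(3) example (64% against 70 to 74%). Nor is the t-test immune to skew: it reaches 7.5 to 7.7% at skewness 2 and 12.4% for lognormal differences. Finally, a normality threshold, or an estimate to accompany Wilcoxon, could properly be left to the SAP. All of that stands, except that the SAP cannot excuse the rule itself. The protocol states the switch and its trigger, so the fault lies in what is fixed and not in what is absent.

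A reader might infer that the switch raises the false-positive rate whenever it is triggered. The documents do not support that. The written trigger looks at IOP in each condition, and skewed IOP is compatible with symmetric differences. In the symmetric scenarios Wilcoxon rejected in 4.8 to 5.1% of the trials that triggered. Inflation needs asymmetric differences whose mean is zero. The protocol neither states nor excludes this; the fixed visit order in section 5 only means that exchangeability is not guaranteed.

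A reader might also infer that the 1.5 mmHg criterion is unusable on the Wilcoxon branch. A threshold in mmHg applies to an estimate and not to a P value from either test, and nothing forbids reporting the mean as well. The defect is that the text as written substitutes the median.

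**Conclusion.** The point holds in a limited form. Two parts need no distributional assumption: the test of the primary endpoint is chosen from the outcome data by an unblinded reading without a threshold, and one of the two branches tests and summarises something other than the mean named in section 4.1.1. The histograms also show each condition and not the paired differences on which both tests depend. Plotting the differences would correct that but leave the change of target.

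The effect on error rates is secondary. If the differences are skewed with mean zero, the written rule adds up to about 2 percentage points over the t-test at skewness 1 to 2, and more if the trigger is applied to the differences. If they are symmetric it adds nothing. These sizes rest on assumed gamma differences, assumed SDs of 2 to 3 mmHg, two-sided testing, and Shapiro-Wilk in place of a visual check. Severity is modest.

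**What to change.** In sections 5.2.1 and 5.2.2, name the paired t-test, reported as the mean difference with its 95% confidence interval, as the single primary analysis whatever the histograms show. Remove the normality-based switch for the primary outcome. Exempt that outcome from the median rule in section 5.2.1 (General), so that the mean is always available to set against 1.5 mmHg. Keep the Wilcoxon signed rank test, with the Hodges-Lehmann estimate, as a labelled sensitivity analysis, and plot the paired differences for description only.

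The change takes a few sentences and adds no patients, visits or data. It has two limits: some power is lost if the differences are heavy-tailed, and strong skew still leaves the t-test somewhat above 5%. The sensitivity analysis would show a reader when the first of these matters.
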